A Pragmatic Randomized Multiple Baseline Trial Evaluating Knowledge Insight Tools (KIT), a Cognitive Behavioural Therapy-informed School-based Counselling Intervention for Secondary School-aged Children and Young People with Anxiety and Mood Difficulties in the UK

Statistical Analysis Plans

NCT ID: Not yet assignment

Document Date: 01/08/2023

Statistical methods

Statistical methods for primary and secondary outcomes {20a}

Primary Outcome

The primary outcome is YP-CORE scores, assessed weekly throughout the baseline and intervention phases. We will analyze within-person and between-person change in YP-CORE scores using descriptive and inferential statistics suitable for multiple baseline designs.

Descriptive methods include summary statistics (e.g., measures of central tendency and dispersion) and visual analysis, where we will inspect time-series graphs of session-by-session scores for stability during the baseline phase, negative trends in the intervention phase, variability within and between phases, and the general degree of overlap between baseline and intervention scores using range lines (Lane & Gast, 2014).

Inferential methods include piecewise multilevel growth models to estimate within-person and between-person differences in average scores (i.e. levels) and the direction/rate of change in scores (i.e. slopes) between the baseline and intervention phases (e.g., Reut et al., 2023). Models will include at least two levels, with repeated observations of YP-CORE scores at level 1 nested within each young person at level 2. We will include additional levels if there is significant variation associated with specific therapists, schools, or regions. We will estimate fixed effects, which include intercepts and slopes averaged across young people for both the baseline and intervention phases (see below for piecewise coding of phases). We will also estimate random effects, which include between-person variation in intercepts and slopes for the baseline and intervention phases.

Two dummy-coded variables each representing an intercept for the baseline phase and intervention phase will be included in the model at level one. Each intercept variable will be coded to reflect the individually-varying break-points between baseline and intervention phases. Take, for instance, a young person with a three-

week baseline phase followed by a four-week intervention phase. The baseline intercept variable for this young person would be coded as 1, 1, 1, 0, 0, 0, 0, and the intervention intercept variable as 0, 0, 0, 1, 1, 1, 1. This coding will produce estimates of the mean baseline and intervention YP-CORE scores averaged across young people with individually varying phase lengths. Baseline and intervention intercepts can then be compared using a two-tailed Wald test to estimate a treatment effect; mean YP-CORE scores during the intervention phase are predicted to be significantly lower than mean YP-CORE scores during the baseline phase.

Two more dummy-coded variables will be included at level one to estimate the slopes for the baseline and intervention phases. The baseline slope variable will be coded for the weeks until the first intervention session, whilst the intervention slope variable will be coded for the weeks since the first intervention session. Continuing the example above of a young person with a three-week baseline phase and four-week intervention phase, the baseline slope variable would be coded as -3, -2, -1, 0, 0, 0, 0, and the intervention slope variable would be coded as 0, 0, 0, 0, 1, 2, 3. Note that the first intervention session is coded as a '0' across baseline and intervention time variables because it serves as the pre-treatment baseline (since the YP-CORE will be administered at the beginning of the first intervention session, before the intervention starts). This coding will produce estimates of the mean slopes during the baseline and intervention phases; a baseline slope not significantly different from zero, plus a significant negative intervention slope, would indicate a treatment effect. Furthermore, random intercepts and slopes will allow us to quantify stability and intraindividual variability in YP-CORE trajectories that would be observed in the visual analysis.

Between-person covariates, including the randomly allocated start week, absolute time in weeks since the first participant was recruited, age, sex, ethnicity, free school-meal eligibility, and special education needs status, will be added to level two of the model to control for the confounding effects of method variables and demographics. We will also include interactions within time variables to investigate non-linear trajectories in YP-CORE scores, and interactions between time and demographic variables to investigate whether demographics moderate the treatment effect.

Multilevel models tend to be robust to deviations from their parametric assumptions (Maas & Hox, 2004). However, we will explore non-parametric alternatives, like Simulation Modelling Analysis (e.g., Dunn et al., 2019), if our data heavily violate these assumptions.

We will also estimate treatment effects and their effect size in line with standard outcomes reported in randomized controlled trials. For the treatment effect, we will use randomization tests, which, unlike more common tests of repeated measures like paired *t*-tests, do not make distributional assumptions or assume homogeneous variances (Bulté & Onghena, 2009). This is because the sampling distribution is based on random permutations of the observed data (i.e. a randomization distribution). We will also calculate a measure of effect size: Shadish et al.'s (2014) adapted *d*-statistic for single-case designs or Tau-U if there are trends in the baseline phase (Manolov, Losada, Chacón-Moscoso, & Sanduvete-Chaves, 2016).

Secondary Outcomes

Secondary outcomes include the RCADS, KIT Fidelity Checklist, and Implementation Survey. The RCADS will be completed at the start, middle and end of the intervention. We will use measures of central tendency and dispersion (e.g., means and standard deviations) to report group-level differences in scores between the baseline and intervention phases. Furthermore, we will evaluate the statistical significance of the difference in group means using parametric tests (e.g., repeated *t*-test), non-parametric (e.g., Wilcoxon Signed-rank test) tests, and regression models controlling for covariates, and quantify the size of the difference using the standardized mean difference (i.e. Cohen's *d*).

We will also calculate Jacobson and Truax's (1991) clinically significant and reliable change indices for the RCADS. Clinically significant change tells us the proportion of young people who start the intervention in the clinical range and finish the intervention in the non-clinical or recovery range. There are different methods for calculating the thresholds for clinical and non-clinical/recovery ranges. We will use the RCADS' established clinical norms to determine the clinical range (e.g., *T* scores

> 69) and non-clinical range (e.g., T scores < 65; Chorpita, Moffitt, & Gray, 2005).

Reliable change refers to whether the changes observed in scale scores (both improvements and deteriorations) over the course of an intervention are greater than the change expected due to measurement error alone (Jacobson & Truax, 1991). We will calculate the proportion of young people who demonstrate reliable improvement, reliable deterioration, and no reliable change in the RCADS after receiving KIT. We will calculate reliable change indices from the sample data using Jacobson and Truax's (1991) formula for reliable change. We will also compare our findings to previous reports of reliable change indices for the RCADS (Edbrooke-Childs, Wolpert, Zamperoni, Napoleone, & Bear, 2018). Finally, we will determine the proportion of young people who showed both clinically significant and reliable change, since one can show reliable improvement without it being clinically significant, and vice versa.

The Fidelity Checklist will be scored in various ways. Traditionally, clinical researchers calculate an index of the proportion of practitioners demonstrating a prespecified level of treatment fidelity. For each KIT intervention with a young person, we will calculate proportions of completeness for each KIT phase across sessions and a total completeness score. That is, we will score the presence of each item on the checklist as a '1' and calculate the proportion of items scored within each phase. Only the first instance of the item throughout the intervention will be counted, not the frequency of the item across sessions. We will also create a total score by summing the subscale scores together. We will then determine a threshold for a 'complete' KIT intervention (e.g., scoring at least 75% of items within each subscale, across all subscales), and determine the proportion of KIT interventions meeting this threshold. This will allow us to conduct sensitivity analyses with complete KIT interventions only vs. incomplete KIT interventions. Since fidelity data will be assessed over time, we can also control for session-by-session fidelity scores in the multilevel growth models of YP-CORE trajectories or analyze patterns/profiles of scores on the fidelity checklists that predict better outcomes.

As for the Implementation Survey, we will use measures of central tendency and dispersion to get an overall sense of how practitioners experienced implementing

KIT. We will also examine the distribution of responses for each item to determine what practitioners favoured most/least about KIT. Some questions, e.g., confidence around delivering KIT, can be used as moderators in the multilevel growth curve models. Depending on the number and richness of responses, we will analyze free-text responses with thematic analysis to draw out practitioners' views of the advantages and barriers to delivering KIT.

Interim analyses {21b}

We will estimate the sample's conditional power after recruiting 50% of the target ($N = 30$) or if we have not met our recruitment target by the first deadline (February 2024), whichever comes first. If the conditional power estimate indicates that we need more participants than the initial target of 60, we will extend recruitment to a second wave with an adjusted alpha level for subsequent analyses.

Stopping guidelines will be based on an O'Brien-Fleming-like alpha-spending function (Ciolino, Kaizer, & Bonner, 2023). We will use the weights outlined by O'Brien-Fleming for our sample size re-estimation analysis pre-specified above (e.g., after we have recruited 50% of our sample), but will pair this with a spending function that is based on the amount of data collected at the time and does not require a pre-specified time-point (so we can re-estimate the required sample size if we have not reached at least 50% of our sample by February 2024).

We will also conduct safety checks by examining trends in the YP-CORE data, particularly if we encounter multiple adverse events. Safety checks will involve visual analysis of YP-CORE scores for each participant during the baseline and intervention phases to assess for any consistent, statistically reliable and clinically significant negative trends. Reliable and clinically significant deterioration in YP-CORE scores that can be linked to the trial protocol will be raised with Adverse Events Oversight Group, who will decide on whether to discontinue the trial.

Methods for additional analyses (e.g. subgroup analyses) {20b}

We will examine (and control for) group differences in demographics and random baseline period by including these variables as covariates in the multilevel growth models. We will also conduct sensitivity analyses that exclude young people whose KIT interventions did not meet fidelity requirements as well as young people who did not start the intervention on their allocated start week, either because they/their practitioner did not attend the intervention session or the first intervention session fell on a school closure and was moved to a another date.

Methods in analysis to handle protocol non-adherence and any statistical methods to handle missing data {20c}

We will analyze all available outcomes on an intention-to-treat basis, including young people who did not start the intervention on the randomly allocated start week (e.g., due to school closures or pupil/practitioner absences) or complete the intervention. Missing data patterns will partly be caused by different baseline and intervention lengths; however, multilevel models can handle missing data due to varying treatment lengths (Ferron, Bell, Hess, Rendina-Gobioff, & Hibbard, 2009). We will assess whether clinical variables (e.g., baseline symptom scores), the randomly allocated start week, and demographic variables, predict dropout. Depending on proportion of missingness (e.g., >30% of observations) and its implied mechanisms, we will run a sensitivity analysis whilst handling missing data with methods such as multiple imputation.

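### With slopes in the model, the two phase intercepts are fitted values at the first session, not phase means, so their Wald test does not test the stated prediction about mean scores

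*SAP*

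**What the plan says.** All of this is in SAP section {20a}, Primary Outcome. The piecewise multilevel growth model is to have "fixed effects, which include intercepts and slopes averaged across young people for both the baseline and intervention phases".

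The first coding paragraph defines two dummies. For a young person with 3 baseline and 4 intervention weeks they are 1,1,1,0,0,0,0 and 0,0,0,1,1,1,1. Of these it says: "This coding will produce estimates of the mean baseline and intervention YP-CORE scores averaged across young people with individually varying phase lengths". It continues: "Baseline and intervention intercepts can then be compared using a two-tailed Wald test to estimate a treatment effect". The prediction attached to that test is that "mean YP-CORE scores during the intervention phase are predicted to be significantly lower than mean YP-CORE scores during the baseline phase".

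The next paragraph adds the time terms: "Two more dummy-coded variables will be included at level one to estimate the slopes for the baseline and intervention phases". In the same example they are -3,-2,-1,0,0,0,0 and 0,0,0,0,1,2,3. On the zero point it says: "Note that the first intervention session is coded as a '0' across baseline and intervention time variables because it serves as the pre-treatment baseline", the reason being timing: "since the YP-CORE will be administered at the beginning of the first intervention session, before the intervention starts".

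The section describes no centring of time within phases, no marginal-mean contrast and no separate model with the dummies alone.

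**The concern.** A phase dummy estimates a phase mean only if no time term for that phase is in the model. Once a slope is added, the dummy's coefficient is the expected score where the time variable is zero. Here both time variables are zero at the first intervention session, so the Wald test compares two fitted lines at that session. The prediction is about average scores over each phase, which is a different quantity.

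This is the first contrast the section offers as an estimate of the treatment effect on the primary outcome. Followed literally, the report would present a gap between two lines at one session as a difference in mean YP-CORE score. A null result could be read as no change in mean score when the means had clearly fallen. The section also gives no rule for the case where this test and the slope criterion disagree, and under a gradual benefit they will.

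**Working it through.** **Inputs.** The four coded variables of the 3+4-week example, as printed in the SAP. The SAP gives no numerical result on this point, so there is none to reproduce. The score series below are noise-free illustrations.

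**Step 1: what each intercept is made of.** The four columns have rank 4, so the model is estimable. Least squares gives these weights on the weekly scores:

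- Baseline intercept: -0.667, 0.333, 1.333 on the three baseline scores. A mean would need 1/3 each.
- Intervention intercept: 0.7, 0.4, 0.1, -0.2 on the four intervention scores. A mean would need 1/4 each.

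The baseline weights are those of an extrapolation one week past the last baseline score.

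**Step 2: intercept difference against phase-mean difference.**

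| Series (3 baseline, 4 intervention) | Intercepts | Difference | Phase means | Difference |
|---|---|---|---|---|
| A. Flat, straight fall: 20,20,20,20,18.5,17,15.5 | 20, 20 | 0 | 20, 17.75 | -2.25 |
| B. Flat, step: 20,20,20,20,16,16,16 | 20, 18.8 | -1.2 | 20, 17 | -3.0 |
| C. Rising, step: 17,18,19,20,16,16,16 | 20, 18.8 | -1.2 | 18, 17 | -1.0 |
| D. Falling, step: 23,22,21,20,16,16,16 | 20, 18.8 | -1.2 | 22, 17 | -5.0 |
| E. Steady fall, no effect: 23,22,21,20,19,18,17 | 20, 20 | 0 | 22, 18.5 | -3.5 |

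Worked for C: baseline intercept = -0.667×17 + 0.333×18 + 1.333×19 = 20; intervention intercept = 0.7×20 + (0.4 + 0.1 - 0.2)×16 = 18.8.

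In B, C and D the intercept difference stays at -1.2 while the phase-mean difference runs from -1.0 to -5.0. With the two dummies alone, series A gives 20 and 17.75, as the SAP's sentence says.

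**Step 3: dependence on the number of sessions.** The zero in A holds for any intervention length, because a line that starts to fall at session 1 still passes through the baseline level there. The step result does depend on length. With n sessions and a flat baseline, the share of the phase-mean difference that the intercept difference recovers is (n - 2)/(n + 1):

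- n = 4: 2/5 = 40% (-1.2 of -3.0)
- n = 6: 4/7 = 57% (-1.9 of -3.3)
- n = 10: 8/11 = 73% (-2.6 of -3.6)

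**Step 4: a contrast that does match the prediction.** Take (intervention intercept - baseline intercept) + mean intervention time × intervention slope - mean baseline time × baseline slope. In the example the mean times are 1.5 and -2, so the added part is 1.5 × intervention slope + 2 × baseline slope:

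- A: 0 + 1.5×(-1.5) + 2×0 = -2.25
- B: -1.2 + 1.5×(-1.2) + 2×0 = -3.0
- C: -1.2 + 1.5×(-1.2) + 2×1 = -1.0
- D: -1.2 + 1.5×(-1.2) + 2×(-1) = -5.0
- E: 0 + 1.5×(-1) + 2×(-1) = -3.5

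Each equals the phase-mean difference.

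**Step 5: consequence for the test, as illustration.** N = 60 is the SAP's target. The rest is assumed: baselines of 3 to 6 weeks, 7 intervention scores, random-intercept SD 5, intervention-slope SD 0.3, residual SD 4. With a true gradual effect of -0.5 points per week, a two-sided 5% Wald test rejects in 5.0% of trials for the intercept contrast (its type I error rate), 99.4% for the phase-mean contrast and 99.7% for the intervention slope.

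**The case against.** **The sentence may describe a model without slopes.** The dummies, the statement about means and the Wald test form one complete paragraph before any slope is coded, and the section speaks of models in the plural. If the model is built in stages, the statement is true. This cannot be excluded, so the fix begins with it. It is weakly supported: the section lists intercepts and slopes together as fixed effects, the slope paragraph adds to the variables already at level one, and no dummies-only model is named.

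**The intercept contrast has a merit.** Under a steady decline with no treatment effect (series E) it is correctly 0, while the phase-mean contrast gives -3.5. That stands. It shows that the two quantities answer different questions. It does not make the SAP's description of the first one right.

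**The plan has other routes to an effect.** A reader might infer that a gradual benefit would go undetected. The SAP does not support that. It separately counts a flat baseline with a significant negative intervention slope as evidence of an effect, and it plans randomization tests and effect sizes. It does not rank the intercept test above these.

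**A reader might also call the contrast a pure pre-treatment gap.** That too goes beyond the coding. Treated scores carry weights 0.4, 0.1 and -0.2, and in series B the contrast is -1.2 although the session-1 score lies exactly on the projected baseline.

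**Conclusion.** The point holds for the four-variable model that the section describes. The stated meaning of the intercepts is wrong, and the Wald test compares the two fitted lines at session 1 instead of the phase means. That difference is 0 for any straight-line fall starting at session 1 and recovers only part of a step: 40% of the phase-mean difference in the 3+4 example, more with more sessions. It is not always the smaller of the two, as series C shows, so it cannot be defended as a conservative version of the mean comparison.

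The algebra rests only on the printed coding. The step figures rest on the example's phase lengths, and the rejection rates on assumed variance components. The defect is a mislabelled estimand and test that should be corrected before analysis.

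**What to change.** 1. State first whether the Wald test belongs to a separate model holding only the two dummies. If so, say that and keep the sentence about means.
2. If it belongs to the four-variable model, delete the phase-mean description and relabel the contrast as the difference between the two fitted lines at session 1.
3. Test the mean-score prediction with the contrast in step 4 of the working.
4. Fix the mean times in advance, because with varying phase lengths the choice matters. For assumed baselines of 3, 4, 5 and 6 weeks in equal numbers, the mean baseline time is (-2 - 2.5 - 3 - 3.5)/4 = -2.75 if each person counts equally, but -(6 + 10 + 15 + 21)/18 = -2.89 if each observation does.
5. Do not present centring time within each person's phases as equivalent. The two match when all participants have the same phase lengths. With assumed baselines of 3 to 6 weeks, 6 sessions and a steady fall of 1 point per week, the step 4 contrast gives -(2.5 + 2.75) = -5.25 and the centred version about -5.3; the second figure also depends on the assumed random effects.

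**Cost.** Wording, and a different linear combination from the same fitted model; no new data. The phase-mean contrast has two downsides that the SAP should state. It absorbs any trend already under way (-3.5 in series E, with no effect), so it must be read together with the baseline slope. And because the untreated first session is coded as intervention, a sustained 4-point drop over four sessions shows as -3.0.

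### The first-session YP-CORE is described as pre-treatment but counted in the intervention level, and the SAP does not say which model supplies the Wald test: the contrast is either diluted by 1/k or is not a difference in phase means

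*SAP*

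**What the plan says.** All of this is in the SAP, section {20a}, Primary Outcome.

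- **Aim.** The growth models are to estimate "differences in average scores (i.e. levels) and the direction/rate of change in scores (i.e. slopes) between the baseline and intervention phases".
- **Fixed effects.** "We will estimate fixed effects, which include intercepts and slopes averaged across young people for both the baseline and intervention phases".
- **Intercept variables.** "Each intercept variable will be coded to reflect the individually-varying break-points between baseline and intervention phases". In the example of three baseline and four intervention weeks, the baseline variable is 1,1,1,0,0,0,0 "and the intervention intercept variable as 0, 0, 0, 1, 1, 1, 1". The fourth score, from session 1, therefore counts as intervention.
- **Stated meaning and test.** "This coding will produce estimates of the mean baseline and intervention YP-CORE scores averaged across young people with individually varying phase lengths". Then: "Baseline and intervention intercepts can then be compared using a two-tailed Wald test to estimate a treatment effect". The prediction is a lower mean in the intervention phase.
- **Slope variables.** "Two more dummy-coded variables will be included at level one to estimate the slopes for the baseline and intervention phases". They are -3,-2,-1,0,0,0,0 and 0,0,0,0,1,2,3. Session 1 is 0 on both "because it serves as the pre-treatment baseline (since the YP-CORE will be administered at the beginning of the first intervention session".
- **Slope criterion.** A baseline slope not different from zero together with a negative intervention slope is a second sign of a treatment effect. The same section also plans randomization tests.

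**The concern.** One score has two roles. The text treats the session-1 YP-CORE as untreated, while the intercept variables average it into the treated level. Setting it to time 0 in the slope variables is sound; the difficulty is confined to the intercepts and to what their difference is said to measure.

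The meaning of that difference depends on whether the slopes are in the model. Without them, each intercept is a phase mean. With them, each intercept is the fitted level where its slope variable is 0, and for both that is session 1. The SAP says the coding yields phase means and does not say which model feeds the Wald test.

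At stake is one of the two model-based signs of effect on the primary outcome. It could understate a benefit, or be reported as showing no difference in mean scores when the means did differ.

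**Working it through.** **Inputs.** The four level-1 variables are the SAP's own, for three baseline weeks and k=4 intervention scores (session 1 included). The SAP gives no effect size, SD or general session count, so these are illustrative assumptions: a flat baseline at 20, a 4-point step after session 1, a decline of 1 point per week from session 1, six baseline weeks, and k=6 and 8. The SAP states no figure for this contrast to reproduce; the check is whether the intercepts have the meaning it gives them. Fits are noise-free least squares.

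**Case A: intercepts only.** The contrast is the intervention mean minus the baseline mean. If the effect is 0 at session 1 and sums to S over the remaining k-1 scores, the printed coding gives S/k and coding session 1 as baseline gives S/(k-1). The share kept is (k-1)/k, so the loss is 1/k.

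- Step, k=4: (20+16+16+16)/4 - 20 = 17 - 20 = -3.0, against 16 - 20 = -4.0 recoded.
- Decline, k=4: (20+19+18+17)/4 - 20 = 18.5 - 20 = -1.5, against 18 - 20 = -2.0 recoded.

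**Case B: intercepts and slopes together.** The intervention intercept is the fitted line at session 1.

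- Step, k=4: deviations from 20 are 0,-4,-4,-4 at t=0,1,2,3. Mean t is 1.5, mean deviation -3, Sxx=5, Sxy=-6. Slope = -6/5 = -1.2. Intercept = -3 + 1.5 x 1.2 = -1.2. The baseline intercept is 20, so the contrast is 18.8 - 20 = -1.2.
- Decline: the line is fitted exactly, with slope -1 and contrast 20 - 20 = 0.

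To recover the phase-mean difference from this model one needs (intervention intercept + 1.5 x intervention slope) - (baseline intercept - 2 x baseline slope). For the step that is (18.8 - 1.8) - 20 = -3.0, and for the decline (20 - 1.5) - 20 = -1.5. The plain intercept difference gives -1.2 and 0.

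| Contrast | k=4 | k=6 | k=8 |
|---|---|---|---|
| A, step -4, printed (recoded -4) | -3.00 | -3.33 | -3.50 |
| A, decline -1/week, printed | -1.50 | -2.50 | -3.50 |
| A, decline -1/week, recoded | -2.00 | -3.00 | -4.00 |
| A, loss 1/k | 25% | 17% | 12.5% |
| B, step -4, printed: level | -1.20 | -1.90 | -2.33 |
| B, step -4, printed: slope | -1.20 | -0.57 | -0.33 |
| B, decline -1/week, either coding: level | 0 | 0 | 0 |
| B, decline -1/week, either coding: slope | -1.00 | -1.00 | -1.00 |

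**Check with noise.** A small random-intercept simulation (assumed: 60 young people, 3 to 6 baseline weeks, k from 4 to 8, between-person SD 5, residual SD 3.5, 40 runs) agrees. For -0.75 per week the mean contrasts were -1.87 (A printed), -2.25 (A recoded) and -0.08 (B). The B contrast rejected in 5% of runs and the intervention slope in 100%. For a 3-point step the contrasts were -2.42, -2.92 and -1.64; B rejected in 87.5% and the slope in 95%.

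**The case against.** The strongest reply has four parts.

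1. **The sentence about session 1 justifies a time origin, not phase membership.** Starting the intervention line at the last untreated score is coherent in a piecewise model. This stands, and it is why the slope coding is not criticised. It does not explain why an untreated score sits in the intervention intercept when that intercept is read as a treated mean.
2. **The two harms cannot both occur.** This stands. The SAP describes the intercepts and the Wald test before it adds the slopes, and speaks of models in the plural, so an intercepts-only test remains possible. Listing intercepts and slopes together as fixed effects, and adding the slopes as two more level-1 variables, favours the joint model without settling it.
3. **The zero under a steady decline is not caused by the session-1 coding.** This stands. It appears under both codings, and a zero gap before treatment is the right answer to that question. What is wrong there is calling the gap a difference in means. A reader might infer that recoding session 1 cures it; it does not.
4. **The printed slope test works.** This stands. For the 4-point step with three baseline weeks and residual SD 1, the slope's ratio to its standard error per person is 1.2/sqrt(1/5) = 2.68 at k=4, against 0.69 for the joint intercept contrast. Recoding the joint model would multiply the slope variance by 5/2 = 2.5, 17.5/10 = 1.75 and 42/28 = 1.5 at k=4, 6 and 8, so the recoding should be kept out of that model.

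**Conclusion.** The level test on the primary outcome is wrong or mislabelled as written, and nothing else in the SAP repairs it. If it comes from an intercepts-only model, it understates the effect by 1/k: 25% in the SAP's example, 17% and 12.5% at the illustrative k=6 and 8. If it comes from the joint model, the statement that the coding produces phase means is incorrect, and at k=4 the contrast is -1.2 for a 4-point step and 0 for a steady decline.

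The exact 1/k loss assumes a flat baseline and no effect before session 1; with unequal k it becomes a weighted average over participants. Sizes beyond k=4 depend on session counts that the SAP does not fix.

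A reader might infer that the whole primary analysis fails, or that the coding can manufacture a benefit. The document does not support either. In the patterns tested the coding errors run towards no effect, the slope criterion recovers a linear effect exactly, and the randomization tests are planned separately. The harm is to one of two model-based signs of effect and to how it would be reported.

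**What to change.** 1. **Phase-mean test.** State that the Wald test comes from a separate model without slopes, with session 1 coded as baseline: in the example, 1,1,1,1,0,0,0 and 0,0,0,0,1,1,1. Report the baseline slope with its confidence interval beside it, and state that this contrast is not protected against a trend that continues from baseline into the intervention phase.
2. **Joint model.** Keep the printed coding for the slope criterion. Describe its intercepts as levels at session 1, and do not test their difference as a phase-mean effect.

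**Cost.** A few lines of text and no extra data. With independent errors, the within-person variance of the slope-free contrast, in units of residual variance, is 1/(baseline scores) + 1/(intervention scores):

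| Baseline weeks | Coding | k=4 | k=6 | k=8 |
|---|---|---|---|---|
| 3 | printed | 0.58 | 0.50 | 0.46 |
| 3 | recoded | 0.58 | 0.45 | 0.39 |
| 6 | printed | 0.42 | 0.33 | 0.29 |
| 6 | recoded | 0.48 | 0.34 | 0.29 |

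The worst case is six baseline weeks with k=4: (1/7 + 1/3)/(1/6 + 1/4) = 0.476/0.417 = 1.14, or about 14% more variance. Between-person variance is left out, so these are not sample-size factors.

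The real downside is trend. With three baseline weeks, a drift of -0.5 per week and no treatment effect gives a slope-free contrast of -1.75, -2.25 and -2.75 at k=4, 6 and 8 under either coding. That is why the baseline slope must be reported with it, although so few baseline points give only weak reassurance that the baseline is flat.
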